Cover page for clinicaltrials.gov

Study Title	Determining the Implicit and Rule-based Learning Ability of Individuals With Aphasia to Better Align Learning Ability and Intervention
NCT Number	05119023
Document Description	IRB approved protocol
Document Date	Document version date = 8/30/22

PARTNERS HUMAN RESEARCH COMMITTEE PROTOCOL SUMMARY

Answer all questions accurately and completely in order to provide the PHRC with the relevant information to assess the risk-benefit ratio for the study. Do not leave sections blank.

PRINCIPAL/OVERALL INVESTIGATOR

[name]

PROTOCOL TITLE

Determining the implicit and rule-based learning ability of individuals with aphasia to better align learning ability and intervention

FUNDING

NIH NIDCD R21 DC019203-01

VERSION DATE

Version 7: 8/30/22

SPECIFIC AIMS

Concisely state the objectives of the study and the hypothesis being tested.

The objective of this study is to examine learning in individuals with post-stroke aphasia (acquired language impairment). We aim to determine a behavioral phenotype of learning for people with aphasia (PWA), examining how cognitive-linguistic variables and stroke characteristics (lesion size and location) relate to learning.

To this end, the aims are as follows:

Aim 1. Determine the presence of selective deficits in observational (implicit) and rulebased learning in individuals with aphasia. Participants in our study will be stratified in to one of four learning profiles: learning under (a) both conditions, (b) rule-based conditions only, (c) observational conditions only, and (d) no condition. Pilot work conducted in eighteen individuals with aphasia has identified equal percentages of learners of type a, c and d (20% of pilot participants in each stratification) with 40% showing learning under rule-based conditions only, supporting the hypothesis that differences in learning profile arise among PWA.

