Aim 2. Determine the predictors of observational and rule-based learning, incorporating subject-specific measures of structural brain damage, aphasia severity, attention, verbal working memory and executive function. We will use regression models to determine predictors of observational learning and rule-based learning, evaluating findings against theoretical frameworks. We predict that preservation of the striatum and selective attention will contribute to observational learning ability. Preservation of the prefrontal cortex, verbal working memory and executive function are expected to contribute to rule-based learning ability.

BACKGROUND AND SIGNIFICANCE

Provide a brief paragraph summarizing prior experience important for understanding the proposed study and procedures.

Aphasia is an impairment in the expression or comprehension of language that results from stroke, traumatic brain injury or progressive neurological disease. Research has shown that speech-language therapy, the treatment for aphasia, can significantly improve people's ability to communicate. However, A major challenge facing the field of aphasia rehabilitation is the variable response to intervention; while some patients respond to therapy, others show limited progress.

Partners Human Subjects Research Application Form Version Date: October 15, 2014 One relatively unexplored possibility is that response to intervention is, in part, due to differences among how patients best learn, which we refer to as learning phenotype. Although learning phenotypes have been used to inform rehabilitation treatments in other domains, treatments for aphasia are currently selected almost exclusively based on language abilities with little to no attention to underlying learning abilities. Our overarching hypothesis is that poor alignment of learning ability and language therapy limits progress and contributes to the variability in outcomes.

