assigned a binary value (1 or 0), are normalized from native to MNI space (a standard brain space utilized in imaging studies). The individualized lesion map is subtracted from each brain region of interest (ROI) to yield the volume of spared tissue per ROI. The percentage of spared tissue in each region is calculated by dividing the volume of spared tissue by the total volume of the MNI atlas ROI. We will use MATLAB to identify the union of lesion maps and anatomical ROIs from the MNI template to compute lesion volume and percent spared tissue for each ROI. Percent spared tissue in ROIs will be entered into regression models evaluating predictors of learning.

Cognitive Linguistic Assessments: Language and cognitive assessments will be scored based on norms and methods of administration and scoring provided in testing manuals and publications.

Composite scores of sustained attention, executive function, and auditory-verbal working memory will be computed for entry into regression models.

Data Analyses: Linear regression models will be run to determine the predictors of learning. Separate models will be examined for SRT observational, AGL observational and rule-based and learning. The dependent variable for SRT observational learning will be Cohen's d effect size for the first round of learning computed in Aim 1. The dependent variable for AGL observational learning will be percent correct in testing computed in Aim 1. The dependent variable for AGL observational learning will be percent accuracy obtained in Aim 1. We anticipate that accuracy rates will fall between .2 and .8 which is recommended if accuracy rates are to be used as a dependent variable for a linear regression. If scores fall outside of this range, we will switch to a logistic regression model where number of successes and the total number of trials are incorporated into the analysis.

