Extensive, partially-overlapping neural networks have been identified to support implicit and rule-based learning. In proposed regression models, we first propose to include percent spared tissue in those ROIs that have shown differential activation in observational versus rulebased learning. Thus, for observational learning, the striatum, which shows enhanced engagement in implicit over rule based learning will be included (e.g. Destrebecqz et al., 2005; Peigneux et al., 2000; Schendan et al., 2003) along with composite scores of visual attention, as attention has been found to be important for implicit learning (e.g. Franklin et al., 2016; Seger 1994). We will evaluate the statistical significance of a regression model with two predictors: percent spared tissue in the striatum and cognitive scores of attention, evaluating the statistical significance of the model and variability accounted for.

For rule-based learning, studies have identified the prefrontal cortex as an important neural substrate that shows increased engagement in rule-based relative to observational learning (e.g. Byrne et al., 2016; Milton et al. 2009; Panuikov & Davis, 2018; Tracey et al., 2003). Verbal working memory and executive functions also play a rule in rule management and shifting (e.g. Carpenter et al., 2016). Thus, we will evaluate the statistical significance of a regression model with three predictors: percent spared tissue in the prefrontal cortex and cognitive scores of working memory and executive function, evaluating the statistical significance of the model and variability accounted for.

Power estimations and justification of sample size. Power analysis for a multiple regression with two predictors was conducted in G*Power to determine a sufficient sample size using an alpha of 0.05. Using an effect size $f^2 = 0.25$, based on correlations of .38 between striatal activation and implicit learning (Peigneux et al., 2000) and on correlation values of .32 between attention and implicit learning from pilot data, with a sample size of 50 we will have power greater than .90 to detect significant effects.

For rule-based learning, a power analysis was conducted in G*Power including 3 predictors. An effect size f² of .28 was estimated based on correlations between prefrontal

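### Lesion size is part of the study objective but is in no specified Aim 2 model, so a significant striatum or prefrontal model cannot by itself support a location-specific claim

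*Combined protocol and SAP*

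**What the plan says.** The opening of the Specific Aims sets the objective as "examining how cognitive-linguistic variables and stroke characteristics (lesion size and location) relate to learning". Aim 2 then promises predictors "incorporating subject-specific measures of structural brain damage, aphasia severity, attention, verbal working memory and executive function", and predicts that preserved striatum will help observational learning and preserved prefrontal cortex will help rule-based learning.

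In the Aim 2 methods, under Calculations of lesion volume and spared tissue, each participant's binary lesion map is subtracted from each region of interest (ROI), and software is used "to compute lesion volume and percent spared tissue for each ROI". The next sentence names what goes forward: "Percent spared tissue in ROIs will be entered into regression models evaluating predictors of learning".

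Data Analyses calls for separate models for SRT observational, AGL observational and rule-based learning. The predictor sets that follow are:

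- observational learning: "a regression model with two predictors: percent spared tissue in the striatum and cognitive scores of attention"
- rule-based learning: "three predictors: percent spared tissue in the prefrontal cortex and cognitive scores of working memory and executive function"

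Each model is to be judged on its overall significance and the variability it accounts for. The paragraph opens "In proposed regression models, we first propose to include percent spared tissue in those ROIs", which hints at later models, but none is described. No covariate list or sensitivity analysis mentions lesion volume.

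**The concern.** Two things are at stake.

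First, lesion size is named in the objective and then receives no analysis. Nothing in the specified models would estimate its relation to learning.

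Second, the Aim 2 predictions are about location. Sparing is the region minus the lesion, so it carries both where the lesion lies and how large it is. If larger strokes impair learning for reasons unrelated to the region, participants with less spared striatum or prefrontal cortex will still tend to learn less. With one region per model and no size term, the model has no means of telling the two explanations apart, and the result could be reported as support for a regional mechanism.

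**Working it through.** **1. The plan's own figures.** Inputs are from Power estimations and justification of sample size. The method is the noncentral F test of overall R², with λ = f² × N, numerator df = k and denominator df = N − k − 1.

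- Rule-based (k=3, f²=.28, N=49, alpha .05): λ = 13.72, power .858. The smallest N for 85% power is 49, as stated.
- Observational (k=2, f²=.25, N=50, alpha .05): λ = 12.5, power .875. The plan states more than .90. That shortfall is a separate matter, but .875 is the baseline used below.

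**2. What an omitted size effect does to the planned test.** The documents give no correlation between sparing, lesion volume, attention and learning, so these are assumptions, in absolute value:

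- s, sparing with volume: .3 to .8
- b, volume with learning: .2 to .5
- a, attention with volume: .3
- no striatal or attention effect on learning other than through volume.

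Induced correlations: sparing–learning r₁ = s·b, attention–learning r₂ = a·b, sparing–attention r₁₂ = s·a.

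R² = (r₁² + r₂² − 2·r₁·r₂·r₁₂) / (1 − r₁₂²)

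Central case, s=.6 and b=.4: r₁ = .24, r₂ = .12, r₁₂ = .18. R² = (.0576 + .0144 − .0104) / .9676 = .064. f² = .068 and λ = 3.4. The planned F on 2 and 47 df rejects in 34% of samples.

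Rejection by the planned two-predictor F, N=50, alpha .05:

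| s | b=.2 | b=.3 | b=.4 | b=.5 |
|---|---|---|---|---|
| .3 | 7% | 11% | 16% | 23% |
| .5 | 10% | 16% | 26% | 40% |
| .6 | 11% | 20% | 34% | 52% |
| .7 | 13% | 25% | 43% | 65% |
| .8 | 16% | 31% | 54% | 78% |

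In the central case the striatum coefficient, adjusted for attention, is significant in about 36% of samples. Attention therefore absorbs little of the size effect under these assumptions.

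**3. What adding lesion volume costs.** At the stated f², with one more predictor:

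- Observational, k=3, N=50: power .822, down from .875. N=54 would give .85 and N=61 would give .90.
- Rule-based, k=4, N=49: power .814, down from .858. N=53 would give .85.

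The variance inflation for the ROI coefficient is 1/(1 − s²), and its square root multiplies the standard error:

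- s=.5: 1.33, standard error up 15%
- s=.6: 1.56, up 25%
- s=.7: 1.96, up 40%
- s=.8: 2.78, up 67%

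Power to detect a true regional effect after adjustment takes the plan's own correlation r as that effect, with volume and the cognitive scores adding nothing: f² = r²(1 − s²)/(1 − r²).

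- Striatum (r=.38, N=50): .81 unadjusted; .69, .53 and .40 at s=.5, .7 and .8.
- Prefrontal (r=.34, N=49): .70 unadjusted; .57, .42 and .32.

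**The case against.** **The listed models may not be the whole plan.** The section is a brief overview, the models are introduced as a first step, and sparing is computed over a wider network. That is fair, and it is why the point is limited to specified models. An undescribed later model still does not protect the described ones.

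**A reader might infer that whole-lesion volume is computed and then dropped.** The documents do not support that. The wording in "to compute lesion volume and percent spared tissue for each ROI" may mean lesion volume within each region. On that reading it equals region volume × (1 − proportion spared), an exact linear function of sparing that could not serve as a covariate. Neither reading puts lesion size in a model.

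**A reader might infer that the planned test is invalid, or that a positive result would be false.** Neither follows. An association between sparing and learning that runs through lesion size is real, and Aim 2 asks for predictors. The 5% benchmark applies only when the result is read as location-specific, which the regional predictions in Aim 2 invite. A test of sparing alone gives larger figures, 18% to 86% for s of .5 to .8 and b of .3 to .5, but the plan does not state that test. Over the same range, with a=.3, the planned F gives about 16% to 78%.

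**A reader might infer that lesion size would produce the predicted result at any region.** It would do so only where sparing tracks volume. At s=.3 the planned F rejects in 7% to 23%, which the documents allow as readily as the larger figures.

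**Adjustment is expensive when collinearity is high.** This stands. Whole-lesion volume also includes the damaged part of the region itself, so the adjusted coefficient is not a pure measure of location. Both facts argue against replacing the planned models, but not against showing results both ways.

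**Conclusion.** The point holds as an omission and a limit on interpretation. Lesion size is in the objective and in no specified model, and a significant striatum or prefrontal model cannot by itself support the regional predictions. That much follows from the text.

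The magnitude does not. The range of about 7% to 78%, with 34% in the central case, depends on correlations the documents do not give and covers everything from a negligible to a dominant size effect. It also assumes linear relations and analysis of 50 scanned participants; the plan enrols 75 and scans a subset whose number is not stated. This should be changed before analysis, but it does not invalidate the planned tests.

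**What to change.** Keep the planned models. For each of the three outcomes (SRT, AGL and rule-based learning), prespecify a companion model that adds whole-lesion volume from the same lesion map, log-transformed if skewed. Volume outside the ROI is a reasonable alternative; choose one in advance. State in the methods which lesion volume is meant.

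Report the lesion-volume coefficient with its interval as the answer to the size question. Show the ROI coefficient with and without adjustment, side by side, and report the observed correlation between sparing and volume. Make a location-specific claim only if the ROI effect holds after adjustment; otherwise describe the result as a predictor that does not separate size from location.

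No new data are needed. The companion models lose about 4 to 5 points of overall power at the stated effect sizes, and the ROI standard error rises by about 15% to 67% for sparing–volume correlations of .5 to .8. At the upper end a null adjusted ROI result would be uninformative, and the report should say so.

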Participants will be tested over three to five sessions during which they will complete: (a) behavioral testing, (b) structural scanning. We anticipate that behavioral sessions (a) and (b) will take around 6 to 7 hours to complete.

- (a) Behavioral testing: Participants will be asked to come to research facilities at the MGH-Institute of Health Professions for behavioral testing. During these sessions, participants will complete standardized cognitive-linguistic assessments and computer-based observational and rule-based tasks, that allow for collection of accuracy, response time and eye gaze data. Most participants are expected to complete behavioral tasks in two to three, two-hour sessions. Some participants may prefer to schedule shorter, and more frequent test sessions and this will be accommodated, and tasks that can be administered over Zoom without affecting data quality (such as those that do not collect response times) can be collected over Zoom if preferred by participants.
- (b) Structural scanning:-The majority of participants will also complete a structural magnetic resonance imaging (MRI) scan in a 3Tesla scanner at the MGH Athinoula A. Martinos Biomedical Imaging Center to obtain structural images of their brain.

In order to participate in brain scans, participants must:

- be safe to participate as determined by the MR eligibility criteria outlined under eligibility, and
- produce scores of learning on at least one behavior learning task that are above chance. Since brain scan data are being utilized to evaluate and predict learning profile, individuals must show learning on at least one task.

High resolution clinical MRI scans from hospitalizations may be available for some participants. These scans will be requested, and if judged to be of high quality (e.g. no evidence of motion artifact, whole brain coverage, axial slices with voxels smaller than 3mm) participants may not need to participate in the structural scan at the MGH Athinoula A. Martinos Center for Biomedical Imaging. Scanning will occur on a separate day or on one of the behavioral testing days.

Eligibility criteria are as follows:

- Be between the ages of 18 and 80 years of age
- Have aphasia due to left hemisphere stroke per report and need for speech language therapy
- Be in the chronic stages of aphasia, at least 6 months post onset of stroke
- Report pre-morbid native-speaker level fluency in American English

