For the AGL Observational learning task (described below), data are collected on the accuracy of match, non-match responses during training computed as a percent correct. Data are also collected as a percent correct score in the testing phase. Each stimulus will be presented two times in testing and accuracy will be coded as 1 (correct) if on both presentations the participant made a correct response. If the item is classified incorrectly on 1 presentation or both presentations, the response for that item will be coded as 0 (incorrect). A threshold probability of 25% will be utilized to characterize performance as above chance and classify a participant as a learner under AGL Observational conditions.

Rule based learning task: For the rule-based task (described below), data are collected on the number of rules learned within the instruction period. Data are also collected on accuracy in testing. An accuracy score is computed for the test phase and is the dependent measure of rule learning. We will compute binomial chance probability. A threshold probability of 50% will be utilized to characterize performance as above chance and classify a participant as a learner under rule-based methods. Any participant whose score does not meet criterion, will be stratified as demonstrating selective weakness in rule-based learning.

Aim 2. Determine the predictors of observational and rule-based learning, incorporating subjectspecific measures of structural brain damage, aphasia severity, attention, verbal working memory and executive function.

Calculations of lesion volume and spared tissue. Implicit and rule-based learning are thought to engage partially overlapping brain networks that include the striatum, dorsolateral prefrontal cortex, medial prefrontal cortex, anterior cingulate, thalamus, medial temporal lobe, superior and inferior parietal cortex, occipital gyrus and cerebellum (e.g.,Destrebecqz et al., 2005; Paniukov & Davis, 2018; Peigneux et al., 2000; Reber, 2013; Schneyer et al., 2009; Squire, 1992; Willingham et al., 2002). The amount of spared tissue within regions of this network will be calculated based on previously established methods (Kiran et al., 2015; Meier et al., 2016; Sims et al., 2016). For each PWA a lesion map, in which the lesioned voxels are

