cortex activation and rule-based learning of 0.34 (Paniukov et al., 2018) and correlations between executive functions, attention and learning that range from .25 to.72 (based on Schnyer et al. 2009 and our pilot work). To achieve 85% power with an alpha of .05 a sample size of 49 is necessary.

Additional participants are included in this IRB to account for potential attrition and the possibility that some participants do not learn tasks limiting the interpretability of results.

Briefly describe study procedures. Include any local site restrictions, for example, "Subjects enrolled at Partners will not participate in the pharmacokinetic portion of the study." Describe study endpoints.

Participants who agree to participate and who provide informed consent will perform 3 to 5, sessions up to 2 hours long. Some participants may prefer to schedule testing over a series of several sessions, which will be accommodated. During these sessions, they will complete:

- SRT Observational (implicit) learning task
- AGL Observational (implicit) learning task
- Rule-based learning task
- Cognitive-linguistic assessments
- Brain Scan

Learning tasks are computer based. Tasks involve looking at pictures, shapes. listening to audio instructions and making button presses. Participants will receive audio and visual instructions. They will complete short practice blocks and have the opportunity to ask questions prior to completing tasks.

Observational (implicit) learning tasks (~ 45 mins):

Observational learning will be evaluated using two tasks: SRT observational learning and AGL observational learning.

The SRT Observational learning task is a classic paradigm, which has been integral to the understanding of implicit learning (see Schwarb & Schumacher, 2012). The SRT that we propose to use to characterize observational learning is a replication of classic SRT tasks first described by Nissen and Bullemer (1987), adapted for eye-tracking by Kinder et al. (2008) and piloted by our team in PWA, young adult and older adult controls. During this task:

- Participants will be seated at least 50 cm from a computer screen with their chin resting on a chin rest.
- The chin rest and chair level will be adjusted for comfort
- The eyetracking camera will be focused on one of the participant's eyes (right eye or dominant eye).
- Four geometric shapes will appear on screen
- A target dot will move from shape to shape

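### If the successes/trials logistic fallback is fitted without allowance for overdispersion and people differ beyond the predictors, its whole-model test can exceed alpha .05; the share of scores that triggers the switch is not stated

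*Combined protocol and SAP*

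**What the plan says.** Under Aim 2, Data Analyses, accuracy outcomes are to be analysed by linear regression, on the expectation that rates will lie between .2 and .8. The fallback, for scores that leave this range, reads: "we will switch to a logistic regression model where number of successes and the total number of trials are incorporated into the analysis". No section mentions overdispersion, a participant effect, a beta-binomial model or robust standard errors.

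The same section names AGL observational learning twice as having an accuracy outcome and never names the rule-based outcome. Applying the fallback to the rule-based model is therefore an inference, though a natural one.

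The result that counts is the whole model. For both the two-predictor and the three-predictor regression the plan speaks of "evaluating the statistical significance of the model and variability accounted for". The power section uses alpha .05, with N = 50 (two predictors) and N = 49 (three predictors).

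The plan expects people to differ. The Aim 1 pilot found unequal learning profiles, "with 40% showing learning under rule-based conditions only", and extra participants are enrolled partly because of "the possibility that some participants do not learn tasks limiting the interpretability of results".

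**The concern.** A plain binomial fit takes the variance of a person's number correct to be m·p·(1−p), where m is the number of items. That is right only if people with the same predictor values have the same true accuracy. If they do not, the scores spread more than the model allows, the likelihood-ratio statistic is too large, and p-values are too small. The planned linear regression estimates its residual variance from the data and so does not have this problem. The switch would remove that protection.

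At stake is whether a significant fallback model for AGL (or, by inference, rule learning) is evidence about spared tissue and cognition, or mainly reflects the fact that some people learned and others did not. How often the question arises depends on the trigger. The plan gives numeric bounds but not how many scores must lie outside them.

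**Working it through.** **The plan's own figures.** Three predictors, f² = .28, N = 49: noncentrality .28 × 49 = 13.72 on 3 and 45 df gives power .858, and 49 is the smallest N for 85%, as stated. The planned effects correspond to R² = .28/1.28 = .219 and .25/1.25 = .20, so about 80% of the variance between scores is left unexplained even if the hypotheses are right. The plan gives no figure for the fallback itself.

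**Inputs from the documents.**
- Non-learners on the rule task at .50: "A threshold probability of 50% will be utilized to characterize performance as above chance and classify a participant as a learner under rule-based methods".
- Non-learners on AGL at .25: "accuracy will be coded as 1 (correct) if on both presentations the participant made a correct response", so an independent guesser scores .5 × .5 = .25.
- Learner mix: the pilot profiles are both 20%, rule only 40%, observational only 20%, neither 20%. A study scan requires participants to "produce scores of learning on at least one behavior learning task that are above chance". Without the no-learning profile, rule learners are (20 + 40)/80 = 75% and observational learners (20 + 20)/80 = 50%.

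**Assumptions, because the documents are silent.** 20, 40 or 60 test items; the learners' true accuracy; predictors unrelated to accuracy (the null). The 50/50 mix for AGL is also an assumption, since the pilot profiles do not name the task.

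**Formula.** With learner share w, learner accuracy pL, non-learner accuracy pN and mean p̄ = w·pL + (1−w)·pN:
- intraclass correlation ρ = w(1−w)(pL−pN)² / [p̄(1−p̄)]
- dispersion φ = 1 + (m−1)ρ
- rejection rate ≈ P(χ²ᵤ > cᵤ/φ), with u predictors, c₂ = 5.99 and c₃ = 7.81. For u = 2 this equals .05^(1/φ).

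**Examples.**
- Rule, learners at .80: p̄ = .725, ρ = .1875 × .09/.1994 = .0846, φ = 2.6/4.3/6.0 for 20/40/60 items. Rates .39/.61/.73.
- Rule, learners at .60: p̄ = .575, ρ = .1875 × .01/.2444 = .0077, φ = 1.15/1.30/1.45. Rates .08/.11/.15.
- AGL, learners at .50: p̄ = .375, ρ = .25 × .0625/.2344 = .0667, φ = 2.27/3.60/4.93. Rates .27/.44/.54.
- AGL, learners at .35: p̄ = .30, ρ = .25 × .01/.21 = .0119, φ = 1.23/1.46/1.70. Rates .09/.13/.17.

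**Simulation of the plain likelihood-ratio test, given a switch** (20/40/60 items):

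| Model | Learners at | Rejection rate under the null |
|---|---|---|
| Rule, N = 49, 3 predictors, 75/25 | .60 | .072/.107/.147 |
| | .65 | .126/.204/.279 |
| | .70 | .189/.343/.456 |
| | .80 | .396/.618/.741 |
| AGL, N = 50, 2 predictors, 50/50 | .35 | .08 to .17 |
| | .40 | .132/.221/.302 |
| | .50 | .272/.441/.551 |
| No differences between people | – | .048 to .057 |

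The formula and the simulation agree. Beta-binomial and logit-normal forms of between-person spread give the same pattern: with 20 items and an intraclass correlation of .05, about .21–.22 (two predictors) and .25–.27 (three). Across these checks, scaling by the Pearson dispersion and using an F test gives .036 to .062.

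**The trigger.** An AGL guesser at .25 scores below .2 with probability .23, .18 or .15 at 20, 40 or 60 items. With 25 guessers among 50, the chance that at least one does so is 1 − .77²⁵, 1 − .82²⁵ or 1 − .85²⁵, more than .98 each time. If any one score is enough, the AGL switch is nearly certain in these settings. If 10% of scores must leave the range, the overall rate for the two-step AGL plan (linear, then switch) is .119/.149/.134 with learners at .40. If only the group mean counts, the switch almost never happens and the rate stays near .05. For rule learners at .60, the any-one reading gives an overall rate of only 5.1–6.7%.

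**Sensitivity.** If AGL guessers repeat their answer at the second presentation (non-learners .50, learners .63–.71), the rate given a switch is 11–43%.

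**The case against.** The best defence is that the plan is silent rather than wrong. The text sits in a brief statistical overview within an IRB summary, and bringing successes and trials into a logistic analysis is compatible with quasi-binomial, beta-binomial or mixed models. A reader might infer that the plan prescribes dispersion fixed at 1. It does not; that is the plain reading and the usual default, no more. What remains is that nothing asks for the allowance the test needs.

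A reader might also infer that the fallback must exceed .05. That does not follow. With no extra-binomial spread the test holds its level, and the documents give no variance. Sorting people by a cut-off is not proof of spread, because a cut-off also splits a sample in which everyone has the same true rate. The case rests on the study's premise and its modest planned R², which make unexplained differences likely but do not measure them.

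Two further limits stand. All participants presumably answer the same items. If those items differ in difficulty, the true within-person variance, Σpᵢ(1−pᵢ), is below m·p̄(1−p̄), and the inflation is smaller than shown. And the complaint that the plan does not say whose scores count is too strong: Aim 1 defines percent-correct scores per participant, so participants' test scores are the natural reading. Only the share is missing.

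**Conclusion.** The point holds, conditionally. Three things must be true together: the switch is made, the model is fitted with dispersion at 1, and true accuracy differs between people beyond what the predictors explain. The false-positive rate of the whole-model test is then above .05. The size rests on assumed item counts, learner accuracies and, for AGL, an assumed learner mix. Given a switch, the range is about 7–15% (rule) or 8–17% (AGL) for mild differences, up to about 74% or 55% for large ones.

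Two sizes should not be read into this. Starting the grid at rule learners of .65 and AGL learners of .40 would suggest a floor of about 13%, but milder differences are plausible and give less. Using the full pilot mix (60/40 for rule) raises the top to about 77%, but the scan-eligibility rule largely keeps the no-learning profile out of the study scan, and so out of models that need spared tissue; only existing clinical scans could bring such people in.

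The planned linear models and the SRT model are untouched. It should be fixed, because the remedy is short and the possible inflation is several-fold. Confidence is medium, because the inputs that set the size are not in the documents.

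**What to change.** Add one sentence to Aim 2, Data Analyses: any logistic model on successes and trials will allow for overdispersion, for example a quasi-binomial fit with Pearson-scaled standard errors and a whole-model F test on N − u − 1 residual df (50 − 2 − 1 = 47 for AGL, 49 − 3 − 1 = 45 for rule). Add a second sentence, before data are seen, stating what share of participants' scores must leave .2 to .8 to trigger the switch. Name the rule-based outcome where AGL now appears twice, so that it is clear which models the fallback covers.

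The cost is larger p-values than a plain binomial fit would give. Sample size, design and data collection do not change. Dropping the switch and keeping the linear model would also work, but is not needed.
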